9.3.5. Clinical Laboratory Assessments

Blood samples for serum chemistry and hematology will be obtained after an eight-hour fast.

The study investigator should monitor subjects during the study for signs of hepatic abnormality potentially meeting the stopping criteria ([Section 11](#)).

The investigator will review clinical laboratory test results as they become available, for determination and documentation of clinical significance (if there are out of range values). The investigative site will contact the medical monitor for any liver function test results that potentially meet the stopping criteria. Possibly drug-related or clinically significant abnormal values of uncertain causality must be repeated. Persistent abnormal laboratory values should be followed at the investigator's discretion. Abnormal liver function tests (specified in [Section 11](#)) must be repeated within 48-72 hours.

Hematology assessments will include hemoglobin, hematocrit, red blood cell count, white blood cell count, differential (neutrophils, lymphocytes, monocytes, eosinophils, and basophils) and platelet count.

Chemistry assessments will include glucose, calcium, electrolytes (sodium, potassium, bicarbonate, chloride), phosphorus, blood urea nitrogen (BUN), creatinine, albumin, total protein, magnesium, alkaline phosphatase (ALP), aspartate aminotransferase (AST), alanine aminotransferase (ALT), lactate dehydrogenase, gamma-glutamyl transferase (GGT), albumin, total bilirubin, direct bilirubin, indirect bilirubin, uric acid, and C-reactive protein (CRP). A thyroid panel (TSH, T3, T4, and free T4) will also be collected at Visit 1.

Qualitative urinalysis will include pH, specific gravity, glucose, ketones, protein, blood, leukocyte esterase, urobilinogen, nitrites, and reflex microscopy.

Abnormal clinical laboratory tests at screening may be repeated, on a case by case basis, after consultation with the Medical Monitor.

Hepatitis B screening will include both the hepatitis B surface antigen (HBsAg) and the hepatitis B core antibody (HBcAb) testing. If HBsAg and HBcAb are both positive, the subject is not eligible. Additional testing for Hepatitis B surface antibody (HBsAb) will be done in case of a positive test result in subjects for either HBsAg or HBcAb, but not both. Subjects positive for HBcAb and negative for HBsAg, but also negative for hepatitis B surface antibody are not eligible for entry into the study. In addition, if either HBsAg or HBcAb are positive, a confirmatory HBV DNA reflex test will be completed. If the HBV DNA test is positive, the subject will not be eligible.

A history of or a positive test result at Screening for the hepatitis C virus antibody indicating ongoing infection will result in confirmatory testing for hepatitis C_mRNA. Subjects with negative hepatitis C_mRNA will be eligible for entry into the study.

A screening test for HIV will be completed. If the screening test for the HIV antibody is positive, a confirmatory test will be performed.

Female subjects of childbearing potential will receive urine pregnancy tests (human chorionic gonadotropin) at Visit 1, Visit 2, and Visit 6. Testing may be performed at other visits, if clinically indicated.

The urine drug panel will include benzodiazepines, psychoactive cannabinoids (e.g., marijuana, THC), opioids, PCP, cocaine, and amphetamines.

9.3.6. Sheehan Suicidality Tracking Scale (S-STS)

The standard version of the S-STS [Sheehan 2014] is a 16-item scale that assesses the seriousness of suicidality phenomena on a Likert-type scale (0 to 4) ranging from 0 = not at all to 4 = extremely. It also assesses the frequency of key phenomena and the overall time spent in suicidality. The standard version is available in identical clinician- and subject-rated formats. The S-STS accommodates a wide range of time frames. In clinical trials, the frequently used variants are “in the past week”, “in the past month”, “since the last visit”, “lifetime look back”, and “in the past day”.

Suicidality identified after baseline will be recorded as an adverse event.

9.3.7. Abuse and Diversion Assessment

Potentially aberrant drug behavior (i.e., misuse and abuse-related events) will be identified, assessed, and quantified using MADDERS (Analgesic Solutions, Wayland, MA), which consists of a set of forms completed by Investigators or qualified Subinvestigators when potential abuse-related events are identified and upon the completion of each subject's participation in the study. Potential abuse-related events will be adjudicated by an independent committee [Smith 2017; Treister 2016].

Any misuse and abuse-related events will be recorded as adverse events.

9.4. Safety and Pharmacovigilance

9.4.1. Adverse Events – Relationship to Study Drug

An adverse event is any untoward, undesired, unplanned clinical event in the form of signs, symptoms, disease, or laboratory or physiological observations occurring in a human being participating in a clinical study with an Aptinyx study drug, regardless of causal relationship.

Laboratory abnormalities are not considered adverse events unless they are associated with clinical signs or symptoms or require medical intervention. However, a laboratory abnormality (eg, a clinically significant change detected on clinical chemistry, hematology, or urinalysis results) that is independent from the underlying medical condition and requires medical or surgical intervention, or leads to study drug interruption or discontinuation, must be considered an adverse event.

The causality of each AE should be assessed and classified by the Investigator as “related” or “not related.” An adverse event is considered related if there is a reasonable possibility that the event may have been caused by the study drug under investigation (i.e., there are facts, evidence, or arguments to suggest possible causation). There is also a timely relationship to the administration of the investigational drug and the event follows a known pattern of response for which no alternative cause is present.

Not Related

- There is no reasonable possibility that the study drug under investigation may have caused the event. The event is obviously explained by another cause or the time of occurrence of the AE is not reasonably related to administration of the study medication.

Related

- There is a reasonable possibility that study drug under investigation caused the event (i.e., there are facts, evidence, or arguments to suggest possible causation). There is also a timely relationship to the administration of the investigational drug and the event follows a known pattern of response for which no alternative cause is present.

When an assessment is not provided, the event will be treated as related for purposes of regulatory reporting.

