The serious adverse event report should provide as much of the required information as is available at the time. The following minimum information is required for reporting a serious adverse event: subject identification, reporting source, and an event outcome. Supplemental information may be transmitted using a follow-up report and should not delay the initial report. Aptinyx or its representative may contact the investigational site to solicit additional information or to follow-up on the event.

If there is any doubt whether the information constitutes a serious adverse event, the information will be treated as a serious adverse event for the purposes of this protocol. Serious adverse event reporting will begin at the time of consent and will end 30 days after the last dose.

All relevant documentation pertaining to a serious adverse event (eg, additional laboratory tests, consultation reports, discharge summaries, and postmortem reports) will be provided to the Sponsor -designated Medical Monitor in a timely manner. Serious adverse events will be

followed until resolution or return to baseline (when worsening of a pre-existing condition is reported). If a serious adverse event does not return to baseline but reaches a stable situation that is not expected to change, this may be documented on the serious adverse event form.

The Sponsor may break the treatment code for subjects who experience a serious adverse event in order to determine if the individual case or group of cases requires expedited regulatory reporting. Individual treatment codes will be available to limited staff who are responsible to break codes for reporting purposes.

For each SAE, the Investigator and Sponsor will independently assess whether there is a reasonable possibility that the event may have been caused by the study drug (“drug-related”). The Sponsor will evaluate each drug-related SAE to determine if the event was unexpected. If the SAE is assessed to be both drug-related and unexpected, the Sponsor or designee will notify all Investigators, and will report it to the appropriate regulatory authorities as required by applicable local regulations. The Sponsor or designee will report SAEs, including narratives, to the U.S. FDA and local regulatory authorities as required by 21 CFR 312.32 and the International Conference on Harmonisation (ICH) Guideline for Good Clinical Practice. The Investigator is responsible for notifying his/her respective IRB.

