6.12.1 Adverse Events

Adverse events will be collected from the time of study drug administration through the last day of the subject's participation in the study.

A treatment emergent adverse event (TEAE) is defined as:

- Any AE that has an onset on or after the first dose of study drug, through the last day of the subject's participation in the study
- Any pre-existing AE that has worsened in severity on or after the first dose of study drug, through the last day of the subject's participation in the study

A treatment-related AE is defined as an AE classified by the Investigator as 'Related' to the study drug. If an AE has missing relationship it is assumed to be related to the study drug for analysis purposes.

Maximum severity (Life threatening) will be assumed for an AE with missing severity.

An overall summary table of AE incidence (number and percent of subjects) and number of events, will be presented by treatment group and overall, for the following categories:

- Any TEAE
- Treatment-Related TEAEs
- Serious TEAEs

- Serious Treatment-Related TEAEs
- TEAEs Leading to Study Drug Discontinuation
- TEAEs Leading to Early Withdrawal
- TEAEs Leading to Death

Summaries of TEAE incidence and number of events by SOC and PT will be presented by treatment group and overall, for the following:

- TEAEs
- Treatment-related TEAEs
- Serious TEAEs
- Serious Treatment-Related TEAEs
- TEAEs Leading to Study Drug Discontinuation
- TEAEs by Maximum Severity, (incidence only)
- Treatment-Related TEAEs by Maximum Severity, (incidence only)

The following listings of AEs will be presented in Section 14.3.2 of the CSR:

- Serious AEs
- AEs Leading to Early Withdrawal
- AEs Leading to Death

AE tabulations will be presented by SOC and PT in descending overall frequency of AE incidence and then alphabetically for ties.

All reported AEs will be listed in Appendix 16.2.7 of the CSR.

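### Protocol 9.4.1 adds conditions to 'related' that conflict with its own reasonable-possibility test and with 9.5, and leave some adverse events fitting neither category

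*Protocol*

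**What the plan says.** Protocol 9.4.1 gives two causality categories and no third. Its introductory paragraph starts with a broad test: "An adverse event is considered related if there is a reasonable possibility that the event may have been caused by the study drug". The next sentence adds that the timing fits and that "the event follows a known pattern of response for which no alternative cause is present". The 'Related' bullet repeats both sentences.

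The 'Not Related' bullet says "There is no reasonable possibility that the study drug under investigation may have caused the event", followed by "The event is obviously explained by another cause or the time of occurrence of the AE is not reasonably related to administration" of study medication. An event with no assessment is treated as related for regulatory reporting.

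Protocol 9.5 sets the rule for SAEs. Investigator and sponsor each judge, independently, whether there is a reasonable possibility of causation. Pattern and alternative cause are not mentioned. The section continues: "If the SAE is assessed to be both drug-related and unexpected, the Sponsor or designee will notify all Investigators", with reporting to the authorities.

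Protocol 12.7.1 plans a table of drug-related TEAEs. SAP 6.12.1 fixes the source: "A treatment-related AE is defined as an AE classified by the Investigator as" related, with a missing relationship counted as related.

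**The concern.** The added sentence is joined to the test by 'also' and 'and', and it stands inside the definition of the category. A site that follows it word for word needs four things before it records 'related': a reasonable possibility, suitable timing, a recognised pattern of response, and no other cause. That is much narrower than reasonable possibility, and it is strictest for the event a phase 2 trial most needs to notice, a reaction not seen before with the compound.

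Safety and tolerability is a primary objective (Protocol 5.1, SAP 2.1). Protocol 4 summarises tolerability at up to 200 mg daily for up to four weeks, and this trial treats for 12 weeks, so what counts as a known pattern rests on limited experience, especially after week 4. If sites resolve the wording differently, the related-TEAE tables partly reflect how each site read the definition. The SAP plans no DSMB analyses (section 8), and no sponsor review of causality is described for non-serious events.

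**Working it through.** No arithmetic applies. The check sets the definitions side by side and follows typical events through them.

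| Event | Reasonable possibility alone (9.4.1 lead sentence; 9.5 for SAEs) | All conditions in 9.4.1 'Related' | 9.4.1 'Not Related' |
|---|---|---|---|
| A. Plausible, well timed, recognised pattern, no other cause | related | met | not met |
| B. Plausible, well timed, new for the drug, no other cause | related | not met (pattern) | not met |
| C. Plausible, well timed, recognised pattern, another cause possible but not obvious | related | not met (alternative cause) | not met |
| D. Obviously explained by another cause, or timing unreasonable | not related | not met | met |

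1. **Gap.** Events B and C satisfy neither category when the full text is applied, yet the investigator has only two boxes.

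2. **Conflict within the protocol.** Every SAE is also an adverse event, so the investigator meets both sections. For an SAE of type B, 9.5 gives drug-related while the full 9.4.1 conditions are not met. Section 9.5 also provides expressly for an SAE that is drug-related and unexpected, so its authors did not intend novelty to rule out a causal judgement.

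3. **Direction.** Any event that meets all the 9.4.1 conditions also meets the reasonable-possibility test, but not the reverse. Apart from blank assessments, which are counted as related under either definition, a literal reader's count of related events can only equal or fall below the count under reasonable possibility.

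4. **Reach.** The SAP list of outputs has eight adverse event tables, 14.3.1.1 to 14.3.1.8. Three rest wholly on the investigator's category (14.3.1.3, 14.3.1.5 and 14.3.1.8). The overall summary, 14.3.1.1, uses it for two of its seven categories. The other four (14.3.1.2, 14.3.1.4, 14.3.1.6 and 14.3.1.7) do not use it.

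5. **Size.** Neither document gives an expected count or rate of related events, or the share likely to be of type B or C. No undercount can be calculated.

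**The case against.** The strongest reply is that the lead sentence of 9.4.1 is the operative rule and the sentence after it merely describes a typical related event. On that reading events B and C are related and there is no conflict. Some sites may well read it so. But the sentence is repeated inside the 'Related' bullet, where it reads as part of the definition, and nothing in the protocol marks it as illustrative. Two reasonable sites can reach opposite answers.

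A second reply is that the text leaves a gap and does not direct anyone to 'not related'. This stands. A plausible event fails that definition too, so under-classification is a risk and not a certainty. The missing-data default helps less than it seems, because it acts only when the field is blank and not when a site has ticked a box.

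A third reply is that the consequences are contained, and much of this stands. SAE causality is judged under 9.5 by two parties. Fatal and life-threatening SAEs go to the medical monitor regardless of cause. The liver criteria in Protocol 11 do not use causality. All TEAEs, serious TEAEs and TEAEs leading to discontinuation are tabulated whatever their cause, laboratory data are summarised separately (SAP 6.12.2), and safety is descriptive and collected blind. The sponsor's SAE judgement does not, however, enter the SAP tables, which use the investigator's category alone.

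A reader might go further and infer that an unexpected event can never be related. The documents do not support that. The lead sentence of 9.4.1 and the whole of 9.5 allow it, and neither document equates 'unexpected' with having no known pattern of response.

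Nor are hepatic or dissociative events clean examples of novelty. Protocol 4 lists raised ALT among the commonest TEAEs and describes liver enzyme elevations, and 9.4.2 sets out the dissociative symptoms that staff should look for. For liver events the alternative-cause condition is open to dispute, since every subject is supplied acetaminophen. But it is taken as needed, supply is not use, and many laboratory changes are not adverse events under 9.4.1. The documents do not link the permitted SSRIs to raised ALT.

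Finally, the subject counts in Protocol 4 add to 154 + 301 + 23 = 478, but this should not be quoted as the number exposed to the drug. The 301 is also the number evaluated in a placebo-controlled study, so it appears to include placebo subjects.

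**Conclusion.** The point holds as an internal contradiction and an incomplete classification. Protocol 9.4.1 carries two standards for 'related', 9.5 uses only the broader one, and the full 9.4.1 wording leaves a class of plausible events without a category. The treatment-related TEAE tables may understate drug-related events as a result, mainly non-serious ones.

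This rests on two assumptions: that some sites apply the added sentence as a set of conditions, and that no instruction outside these documents has already settled the reading. It would be wrong to state as fact that drug-related events are under-classified, because events in the gap may be recorded either way. The effect is confined to outputs that use the investigator's category. Total TEAE, SAE and laboratory summaries are untouched, and so are the efficacy analyses.

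**What to change.** In 9.4.1, in both the introductory paragraph and the 'Related' bullet, define 'related' by reasonable possibility alone, as 9.5 does. Keep timing, pattern of response and alternative causes as factors for the investigator to weigh, and say that none of them is required. The definition in SAP 6.12.1 can stay as it is.

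The SAP addendum states that it was written after database lock and unblinding, so this trial's events will already have been classified. For those data the practical step is a caveat on the related-TEAE tables in the study report. It should say that the definition was open to two readings, that the counts may be low, and that the all-causality tables are the safer basis for comparing arms. Reclassifying events after unblinding would introduce a bias of its own and is not advised.

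The cost is one sentence changed in two places, a memo to sites where classification is still under way, and a short note in the report. The downside is that somewhat more events will be classed as related.

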9.4.2. Recording Adverse Events

A “preexisting” condition is one that is present before study drug dosing and is reported as part of the subject’s medical history. Pre-existing conditions should be reported as an adverse event only if the frequency, intensity, or character of the pre-existing condition worsens during the course of the study. Adverse events will be collected from the time of study drug administration through the last day of the subject’s participation in the study.

Subjects should be instructed to report all potential adverse events to the Investigator and should be queried in a nonleading manner, without specific prompting (e.g., “How are you feeling?”). The site study staff should assess emerging symptoms of dissociative reaction similar to those caused by *N*-methyl-D-aspartate antagonists, including memory impairment, disturbance in time, body or environmental perception, stilted speech, emotional withdrawal, impaired coordination, motor retardation, bizarre reasoning or illusory experiences in any sensory perception, or confused state; such symptoms may be captured as adverse events.

To avoid vague, ambiguous, or colloquial expressions, all adverse events should be recorded in standard medical terminology rather than in the subject’s own words. Each adverse event will also be described in terms of duration (start and stop date), severity, relationship to study drug, action(s) taken, and outcome. Diagnoses (rather than symptoms) should be recorded wherever possible.

9.4.3. Reporting Adverse Events

All adverse events must be documented, evaluated, and reported in the source documents and eCRF. Adverse events will be collected from the time of study drug administration through the last day of the subject’s participation in the study. Follow-up of AEs must be conducted in accordance with the investigative site’s normal practice. Ongoing adverse events should be followed to a satisfactory resolution in the Investigator’s opinion. Subjects should be instructed to report all adverse events to the Investigator. In addition, the Investigator should seek to elicit any clinical or objective reactions by specific questioning (e.g., “How have you been feeling?”) and as appropriate by examination. Information on all adverse events should be recorded on the eCRF. All clearly related signs, symptoms, and results of diagnostic procedures performed in relation to an adverse event should be grouped together and recorded as a single diagnosis.

9.4.3.1. Severity of Adverse Events

All adverse events will be assessed for severity, using the following general grading scale:

Mild: Transient or mild discomfort (<48 hours); no medical intervention/therapy required.

Moderate: Mild to moderate limitation in activity – some assistance may be needed; no or minimal medical intervention/therapy required.

Severe: Marked limitation in activity, some assistance usually required; medical intervention/therapy, required hospitalization possible.

Life threatening: Extreme limitation in activity, significant assistance required; significant medical intervention/therapy required, hospitalization, or hospice care probable.

When changes in the severity of an adverse event occur more frequently than once a day, the maximum severity for the experience that day should be noted. If the severity category changes

over a number of days, then those changes should be recorded separately (with distinct onset dates).

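### An adverse event whose grade changes over several days is split into separate records, and the SAP counts events with no rule to rejoin them, so the descriptive event counts (and only those) can be inflated

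*Protocol*

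**What the plan says.** **Recording.** Protocol 9.4.3.1 has two rules for an adverse event whose severity changes. If it changes more than once in a day, "the maximum severity for the experience that day should be noted". If the category changes "over a number of days, then those changes should be recorded separately (with distinct onset dates"), each change becomes a separate entry. Protocol 9.4.2 describes each adverse event by its own start and stop date, severity, relationship, action and outcome, so a separately recorded change with its own onset reads naturally as a further record.

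**Tabulation.** SAP 6.12.1 plans "An overall summary table of AE incidence (number and percent of subjects) and number of events", with seven categories from any TEAE to TEAEs leading to death. It adds: "Summaries of TEAE incidence and number of events by SOC and PT will be presented". Five of those SOC/PT summaries carry an event count. The other two, by maximum severity, are restricted to incidence.

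**Subject-level counting.** Protocol 12.7.1 and SAP 6.3.4 count a subject once per PT and once per SOC; the SAP does so at the highest severity. The TEAE tables in protocol 12.7.1 give numbers and percentages of subjects. The event count is an addition of the SAP.

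**Related wording.** The mild grade reads "Transient or mild discomfort (<48 hours); no medical intervention/therapy required". Protocol 9.4.2 says of dissociative symptoms that "such symptoms may be captured as adverse events", while protocol 9.4.3 says "All adverse events must be documented, evaluated, and reported in the source documents and eCRF".

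**The concern.** The recording rule and the counting rule were written separately and do not fit together. The protocol splits one clinical episode into several dated entries whenever its grade moves from day to day. The SAP counts entries. Nothing visible reconnects them:

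- The once-per-subject rules work on subjects, not events.
- The grouping instruction in protocol 9.4.3 concerns signs and symptoms that belong to one diagnosis, not successive grades of one event.
- The outcome list in protocol 9.4.3.3 has no option for a record closed because its grade changed, so that field does not identify a continuation.
- The post-database-lock addendum leaves SAP 6.12.1 as it was.

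Safety and tolerability is a primary objective, and event counts by arm will be read next to incidence. As planned, the event column partly measures how often grades moved and how strictly sites applied the splitting rule, not only how many events occurred.

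**Working it through.** The documents state no figure for this quantity, so there is nothing to reproduce. The check applies the stated rules to example severity paths.

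**Step 1: records per episode.** Take the maximum grade on each day (within-day rule) and open a new record whenever that daily maximum differs from the day before (across-days rule):

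records = 1 + number of day-to-day changes in the daily maximum grade.

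| Path of one episode | Changes | Records, hence events counted | Subjects counted | Maximum grade |
|---|---|---|---|---|
| Mild throughout | 0 | 1 + 0 = 1 | 1 | mild |
| Mild-moderate-mild within each day | 0 | 1 + 0 = 1 | 1 | moderate |
| Mild-moderate-mild over days | 2 | 1 + 2 = 3 | 1 | moderate |
| Mild-moderate-severe-moderate-mild over days | 4 | 1 + 4 = 5 | 1 | severe |

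The subject count is 1 in every row, and the maximum grade is the same whether or not the episode is split. Incidence and the maximum-severity tables are therefore untouched.

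**Step 2: size across all events.** Let f be the fraction of adverse events that change grade across days and m the mean number of extra records for each of them. Neither is in the documents; both are assumptions. The event count is multiplied by

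factor = 1 + f × m.

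| f | m = 1 | m = 2 | m = 4 |
|---|---|---|---|
| 5% | 1.05 | 1.10 | 1.20 |
| 10% | 1.10 | 1.20 | 1.40 |
| 20% | 1.20 | 1.40 | 1.80 |
| 30% | 1.30 | 1.60 | 2.20 |

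The range is 1 + 0.05 × 1 = 1.05 to 1 + 0.30 × 4 = 2.20.

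**Step 3: with joining.** If the split records of one episode are joined, the third and fourth paths in Step 1 each give one event instead of 3 and 5. Incidence and maximum severity stay as they were.

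**Step 4: the 48-hour limit.** Mild carries a duration limit; moderate is defined by limitation of activity. Discomfort lasting 48 hours or more without limitation fits neither cleanly. A site that regrades it upward changes the maximum-severity tables. Because the category has then changed, it also opens a second record under the across-days rule. This is a grading question first and reaches the event count only by that route.

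**The case against.** The case against giving this weight is substantial.

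- **Recorded separately need not mean a new adverse event.** The eCRF layout is not shown, and the dataset specifications (SAP 6.3.2) and table shells (SAP 6.3.6) are separate documents. A link may exist there. This stands as a caution, but the visible rules, followed as written, produce the multiple count.
- **Nothing inferential depends on it.** Protocol 12.7 makes safety descriptive with no testing, and the protocol's own tables count subjects. This stands and limits the importance of the point.
- **The rate of grade change is unknown.** This also stands, which is why only a range is given.

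A reader might infer more than the documents support:

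- That every severity change creates a new event. It does not: within-day changes collapse to the daily maximum.
- That the splitting distorts incidence or the maximum-severity tables. It cannot: both count each subject once, and the latter carry no event count.
- That it biases the comparison between arms. The recording rule is the same in all arms and the study is double-blind. No document gives a reason for grades to fluctuate more in one arm.
- That recording dissociative symptoms is optional. Protocol 9.4.1 defines an adverse event broadly and 9.4.3 makes recording mandatory, so a dissociative symptom that meets the definition must already be recorded. The permissive sentence can be read alongside the rules on pre-existing conditions and on recording diagnoses instead of symptoms. If it had any effect, it would lower counts, the opposite direction to the splitting.

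On the mild grade, the bracket may qualify only the word *transient*. The text does not settle this.

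**Conclusion.** The concern holds for the event-count columns in SAP 6.12.1 and nowhere else. Under the rules as written, one episode whose grade changes over days is counted as several events, for example three for mild-moderate-mild. Overall inflation is a factor of 1.05 to 2.20 if 5% to 30% of events change grade with 1 to 4 extra records each. It also assumes that sites follow the splitting rule and that no linking is specified outside the two documents. Subject incidence, the maximum-severity tables and all efficacy results are unaffected. The point is modest but real: a reported number would not mean what its label says.

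Two wording matters are separate and minor. The duration limit in the mild grade is ambiguous and can affect the maximum-severity tables. The permissive and mandatory statements on recording in protocol 9.4.2 and 9.4.3 should be made to agree.

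**What to change.** **Main change, SAP 6.12.1.** For event counts only, treat consecutive records of the same PT in one subject as one event when (a) they differ in severity and (b) the recorded stop date of one meets the recorded onset of the next. Dates imputed under SAP 6.2.5 should not qualify. That section sets a stop date known only to the month to the month's last day, and an onset known only to the month to its first day (with exceptions around the first dose and last visit), so two unrelated records in successive months could appear to touch. Give the joined event the maximum severity. Count it as serious, related or leading to discontinuation if any component record is, and treat the overall table's early-withdrawal and death rows in the same way.

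**Alternative.** Drop the event column and report subject incidence only, as protocol 12.7.1 does.

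**Cost.** One derivation rule and a data check so that distinct recurrences of the same PT are not merged. The addendum states that its changes followed database lock and unblinding, so a rule added now would have to be reported as a post-hoc derivation.

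**Minor wording.** In protocol 9.4.3.1, clarify that duration does not determine the grade. Reconcile 9.4.2 with 9.4.3 so that dissociative symptoms meeting the adverse event definition are plainly under the mandatory rule. For this trial, such protocol edits would serve mainly as wording for later protocols.
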